Predictive power monitoring will not be performed for the 2 monotherapy groups (B5 and B6) in dose-expansion Part B and the 1L RM SCCHN patients in Arm B7. The 2 monotherapy arms will continue recruiting until 12 efficacy evaluable patients have been enrolled in each arm.

For the 2 combination arms in the anti-PD-(L)1 pretreated patients (B1 and B2), once efficacy outcomes have been observed in the first 10 efficacy evaluable patients in each arm, a predictive power calculation will be used to assess the chance of observing at least 3 of 20 responses (either PR or CR) in each arm. Predictive power (chance to observe at least 3 of 20 responses) will be recalculated following the observation of the efficacy outcome in each efficacy evaluable patient as they were dosed in the trial. If, following the observation of any patient's outcome, predictive power falls below 20%, the arm in which this happens will be stopped. However, no formal interim analysis will be conducted for the combination arms in the anti-PD-(L)1 pretreated patients.

In addition, Arms B7 and B8 will enroll patients who have not received prior systemic treatment for RM SCCHN and will receive combination treatment of AZD9150 in combination with MEDI4736. With approximately 48 patients in each arm, the chance that

fewer than 12 patients with CR or PR (responding) will be observed, given the true fraction of patients responding is 35%, is 9%. The chance that at least 15 patients responding is observed, given the true fraction of patients responding is 25%, is 20%. In addition, B8 will incorporate predictive power monitoring for futility beginning with the 15th patient. If at any time from the 15th patient through the 48th patient, the chance to observe 13 responses in 48 patients falls below 20%, then the arm will be stopped.

Recruitment will continue while predictive power is measured. If an arm is to be stopped, no new patients will be recruited to that arm, but patients who are already on study in that arm will continue in accordance with study guidelines outlined in Section 4.

TABLE OF CONTENTS

TITLE PAGE.....	1
VERSION HISTORY	2
CLINICAL STUDY PROTOCOL SYNOPSIS	9
TABLE OF CONTENTS.....	25
LIST OF ABBREVIATIONS AND DEFINITION OF TERMS.....	32
1 INTRODUCTION.....	38
1.1 Background and rationale for conducting this study	38
1.1.1 AZD9150.....	38
1.1.2 AZD5069.....	38
1.1.3 MEDI4736.....	39
1.1.4 Tremelimumab	39
1.1.5 Disease background	39

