^a The results are averaged over the corresponding set of naïve and pretreated values. The expected sample size includes 12 patients in each of the 2 monotherapy arms.

Thus, with the study design and interim assessments as described above, the chance to stop a combination arm in anti-PD-(L)1 naïve patients given an optimistic true ORR value (0.45 for naïve and 0.31 for pretreated patients) is approximately 19.3%. The chance to stop a combination arm in anti-PD-(L)1 pretreated patients is approximately 11.7%. If the true ORR performance of the combination arms is low (i.e., approximately 10% for naïve, 5% for pretreated), the chance that any combination will stop before fully recruiting is >98% for naïve and >94% for pretreated.

Figure 9 Adaptive approach to sample size Part B (B1-B6)

If at least 2 CR or PR are observed in the first 20 patients in either of the 2 pretreated expansion arms (Arm B1 or B2), then an additional 25-32 patients may be enrolled.

In addition, Arms B7 and B8 will enroll patients who have not received prior systemic treatment for RM SCCHN and will receive combination treatment of AZD9150 in combination with MEDI4736. With approximately 48 patients in each arm, the chance that fewer than 12 patients with CR or PR (responding) will be observed, given the true fraction of patients responding is 35%, is 9%. The chance that at least 15 patients responding is observed, given the true fraction of patients responding is 25%, is 20%. In addition, B8 will incorporate predictive power monitoring for futility beginning with the 15th patient. If at any time from the 15th patient through the 48th patient, the chance to observe 13 responses in 48 patients falls below 20%, then the arm will be stopped.

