## Statistical Analysis Plan

maximum of 35 efficacy evaluable patients following the interim analysis if at least 5 of 20 patients have responded with at least a PR.

For each combination arm in the anti-PD-(L)1 pretreated patients (Arms B1 and B2); a predictive probability will be calculated to assess the chance of observing at least 3 of 20 responses (either PR or CR) following 10 efficacy evaluable patients in each arm. If the predictive probability falls below 20% within an arm, then the corresponding arm will be stopped. However, no formal interim analysis will be conducted for the combination arms in the anti-PD-(L)1 pretreated patients.

Recruitment will continue while predictive power is measured. If an arm is to be stopped, no new patients will be recruited but patients who are already on study will continue in accordance with study guidelines outlined in Section 4 of the protocol Amendment 9.

If at least 2 CRs or PRs are observed in the first 20 patients in either of the 2 pretreated expansion arms, an additional 25 to 32 patients may be enrolled to that particular pretreated combination arm.

Predictive power monitoring will not be performed for the 2 monotherapy groups (B5 and B6) in dose-expansion Part B. The 2 monotherapy arms will continue recruiting until 12 efficacy evaluable patients have been enrolled in each arm.

In addition, Arms B7 and B8 will enroll patients who have not received prior systemic treatment for recurrent and/or metastatic squamous cell cancer of the head and neck (RM-SCCHN) and will receive combination treatment of AZD9150 in combination with MEDI4736. With approximately 48 patients in each arm, the probability of observing  $\leq 12$  responses (CR or PR) out of 48 patients is 9%; given the true probability of responses is 35%. The probability of observing  $\geq 15$  responses (CR or PR) out of 48 patients is 20%, given the true probability of responses is 25%. In addition, B8 will incorporate predictive power monitoring for futility beginning with the 15th patient. If at any time from the 15th patient through to the 48th patient, the chance to observe 13 responses in 48 patients falls below 20%, then the arm will be stopped.

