In the anti-PD-(L)1 pretreated patients (B1 and B2), approximately 10 to 52 patients will be treated in each of the 2 combination therapy arms. Once efficacy outcomes have been observed in the first 10 efficacy evaluable patients in each arm, a predictive power calculation will be used to assess the chance of observing at least 3 of the 20 responses (either partial or complete) in each arm. Predictive power (chance to observe at least 3 of 20 responses) will be recalculated following the observation of the efficacy outcome in each efficacy evaluable patient as they were dosed in the trial. If, following the observation of any patient's outcome, predictive power falls below 20%, the arm in which this happens will be stopped. However, no formal interim analysis will be conducted for the combination arms in the anti-PD-(L)1 pretreated patients.

In addition, Arms B7 and B8 will enroll patients who have not received prior systemic treatment for RM SCCHN and will receive combination treatment of AZD9150 in combination with MEDI4736. With approximately 48 patients in each arm, the probability of observing  $\leq 12$  responses (CR or PR) out of 48 patients is 9%, given the true probability

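### The 9% chance quoted for arms B7 and B8 does not match the protocol's own event (it is 5.1%), and for B8 the futility rule takes the chance of a stop or a low count to 21–24%

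*Protocol*

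**What the plan says.** Protocol 8.2.2, repeated in the synopsis under Statistical methods, introduces the first-line arms with "With approximately 48 patients in each arm" and gives two probabilities for both. The first is worded as follows: "fewer than 12 patients with CR or PR (responding) will be observed, given the true fraction of patients responding is 35%, is 9"%. Its companion reads "The chance that at least 15 patients responding is observed, given the true fraction of patients responding is 25%, is 20"%.

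SAP 2.2 and 3.6.2 carry the same two probabilities, but attach the first to 12 or fewer responders at a true rate of 35%: "responses (CR or PR) out of 48 patients is 9"%.

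Both documents then add a rule for B8 only: "B8 will incorporate predictive power monitoring for futility beginning with the 15th patient". The trigger is: "If at any time from the 15th patient through the 48th patient, the chance to observe 13 responses in 48 patients falls below 20"%, and the arm then stops. Protocol 8.2.2 says that B7 has no such monitoring. Neither document restates the 9% or the 20% for B8 with the rule in force.

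**The concern.** There are two separate problems.

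1. The protocol and the SAP give one number for two different events, fewer than 12 and 12 or fewer. At most one of them can be right. SAP section 13, which lists departures from the protocol, mentions only the analysis-set definitions, so the difference is not recorded as intended.
2. The 9% and 20% are fixed-sample figures for 48 patients, yet they are given for each arm. B8 is checked after every patient from the 15th onward and may never reach 48, so the figures do not describe it.

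These are the only operating characteristics stated for the first-line arms, and objective response rate is the primary endpoint of Part B. A reader who takes 9% at face value would treat a stopped or low-response B8 as stronger evidence against the flat-dose, every-two-weeks regimen than it is.

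**Working it through.** **Inputs.** N = 48 per arm. True rates are 35% and 25%. The protocol event is X ≤ 11, the SAP event is X ≤ 12, and the upper-tail event is X ≥ 15. The B8 rule checks after each patient from the 15th, has a target of 13 of 48 (read as at least 13), and stops below 20% (Protocol 8.2.2). The predictive-probability formula is in SAP 3.6.2.

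**Step 1: fixed sample of 48, exact binomial.**

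| Event | True rate | Exact | Stated |
|---|---|---|---|
| X ≥ 15 | 25% | 19.99% | 20% (both documents) |
| X ≤ 12 | 35% | 9.43% | 9% (SAP) |
| X ≤ 11 | 35% | 5.10% | 9% (protocol) |
| X ≥ 15 | 35% | 75.4% | not stated |

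The SAP's figure and the 20% both reproduce, so N = 48 and the exact binomial are the intended model. The gap between the two lower tails is P(X = 12) = 4.33%, and 5.10% + 4.33% = 9.43%. Reading 48 as approximate does not rescue the protocol. Fewer than 12 has probability 9.0% only at N = 45, where P(X ≥ 15 | 25%) is 13.3%, not 20%.

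**Step 2: the B8 stopping boundary.** With n patients observed and x responders, the SAP formula is

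PP = Σₖ P(Bin(n, x/n) = k) × P(Bin(48 − n, μₖ) ≥ 13 − x),

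with μₖ = k/n, except 0.5/n at k = 0 and (n − 0.5)/n at k = n. Examples of the result:

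| n | Stop at (PP) | Continue at (PP) |
|---|---|---|
| 15 | 2 (5.8%) | 3 (23.0%) |
| 20 | 4 (18.5%) | 5 (41.8%) |
| 30 | 6 (9.7%) | 7 (26.8%) |
| 40 | 9 (10.1%) | 10 (32.9%) |
| 47 | 11 (0%) | 12 (25.5%) |

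**Step 3: B8 with the rule applied.** Start from the binomial distribution of responders at n = 15. Remove every state with PP < 20% and count its probability as stopped. Add one patient at the true rate, and repeat to n = 48. The SAP says its prior is non-informative without naming it, so a beta-binomial with a uniform Beta(1,1) prior is shown as well.

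| Quantity | SAP formula | Beta(1,1) | No monitoring |
|---|---|---|---|
| True 35%: early stop | 23.0% | 20.2% | – |
| True 35%: early stop, or 12 or fewer at 48 | 23.8% | 21.1% | 9.4% |
| True 35%: 15 or more at 48 | 68.0% | 69.9% | 75.4% |
| True 25%: early stop | 69.4% | 67.1% | – |
| True 25%: 15 or more at 48 | 16.6% | 17.4% | 20.0% |

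In the second row under the SAP formula, 23.0 points are early stops and 0.8 points are full arms ending at exactly 12.

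**Sensitivity.** For the second row, a Jeffreys prior gives 21.3% and Beta(0.01, 0.01) gives 23.8%. Cruder methods that the SAP does not use give 26.0% (normal predictive without continuity correction) and 27.8% (plug-in conditional power). None comes near 9%.

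**The case against.** The case on the other side accepts the arithmetic and argues about meaning and weight.

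- **Only the inequality is off.** The number 9% is sound for 12 or fewer, the SAP has it right, and no decision rule uses fewer than 12. This is a fair account of how the slip probably arose. The protocol's sentence is still false as written and still disagrees with the SAP.
- **The 9% and 20% describe a 48-patient arm before the rule is added.** The order of the sentences allows that reading, but the figures are given for each arm, B8 included. For the other monitored combination arms, Protocol 8.2.2 does state stopping chances with monitoring included (about 19.3%, 11.7%, above 98% and above 94%). B8 is the exception to the plan's own practice.
- **The 21–24% is a composite and not the same event as the 9%.** This is correct, and the early-stop part should be shown separately, as above.
- **The plan sets no success rule for B7 or B8.** This stands. Calling the outcome a false negative would be an interpretation; the plan reports response rate with an exact 80% interval and makes no comparison between arms.
- **A stop ends new recruitment only.** This also stands. Recruitment continues during monitoring, the first scan is at Week 7, and confirmation takes at least 4 more weeks. A stopped arm may therefore hold more patients than the trigger count, and they still contribute data.
- **Enrolment is closed and the response-rate estimate and its interval do not depend on these figures.** This is true, so the correction affects how B8 is described and read, not how it is run.

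**Conclusion.** The concern holds on both counts. As worded in the protocol, the probability is 5.1%, not 9%; the 9% is right for 12 or fewer in an unmonitored 48-patient arm, which describes B7. For B8, at a true response rate of 35%, the chance of stopping early or finishing with 12 or fewer responders is 21–24%, more than twice the stated figure: about one in four or five, where 9% suggests one in eleven. The effect on the 20% figure is smaller, a fall to about 17%.

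The 5.1% needs only N = 48 and independent outcomes with a common response rate. The B8 figures also assume that the target means at least 13 responses, that predictive probability follows the SAP's formula or a beta-binomial with a usual non-informative prior, that the rule is applied without exception, and that each outcome is known before the next check. Delayed outcomes would change how many patients are enrolled when a stop triggers; the documents give no accrual rate from which to size that.

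**What to change.** 1. In the protocol synopsis and 8.2.2, change the event to 12 or fewer and keep 9%, which matches the SAP and fits the B8 target of 13. Alternatively, keep fewer than 12 and state 5%.
2. In the protocol synopsis and 8.2.2, and in SAP 2.2 and 3.6.2, limit the 9% and 20% to B7, or label them as fixed-sample figures without monitoring.
3. In the same places, give B8's properties with the rule applied. At a true 35%: about 20–23% chance of an early stop, 21–24% chance of an early stop or 12 or fewer responders, and 68–70% chance of 15 or more. At a true 25%: 67–69% chance of an early stop and about 17% chance of 15 or more. Name the predictive-probability method and prior, and say that each outcome is taken as known before the next check.

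The cost is wording in two documents and a less favourable stated figure for B8. No extra patients are needed, and neither the futility rule nor the planned analysis of response rate changes.

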Patients with prior anti-PD-(L)1 antibody exposure who have **not** been excluded by the Investigator for treatment with AZD5069 will be assigned via an interactive web-based randomisation system (IWRS) in a 1:1 ratio to 1 of the following 2 treatment arms:

- Treatment arm B1: AZD9150 in combination with MEDI4736 (anti-PD-(L)1 pretreated population)
- Treatment arm B2: AZD5069 in combination with MEDI4736 (anti-PD-(L)1 pretreated population)

ANTI-PD-(L)1 NAÏVE POPULATION

Patients with **no** prior anti-PD-(L)1 antibody exposure who have been excluded by the Investigator for treatment with AZD5069 will be assigned via an IWRS in a 2:1 ratio to 1 of the following 2 treatment arms:

- Treatment arm B3: AZD9150 in combination with MEDI4736 (anti-PD-(L)1 naïve population)
- Treatment arm B5: AZD9150 alone (anti-PD-(L)1 naïve population)

Patients with **no** prior anti-PD-(L)1 antibody exposure who have **not** been excluded by the Investigator for treatment with AZD5069 will be assigned via an IWRS in a 2:2:1:1 ratio to 1 of the following 4 treatment arms:

- Treatment arm B3: AZD9150 in combination with MEDI4736 (anti-PD-(L)1 naïve population)
- Treatment arm B4: AZD5069 in combination with MEDI4736 (anti-PD-(L)1 naïve population)
- Treatment arm B5: AZD9150 alone (anti-PD-(L)1 naïve population)
- Treatment arm B6: AZD5069 alone (anti-PD-(L)1 naïve population)

- Non-randomized treatment arms B7 and B8: AZD9150 in combination with MEDI4736 (anti-PD-(L)1 [flat dose for B8] naïve population) for patients who have not received prior systemic treatment for RM SCCHN.

The dose-expansion Part B will use an adaptive approach to sample size based on Bayesian statistical methodology, so the number of actively enrolling treatment arms may decrease as the study continues. See Section 8.2.2 for details on sample size, conditions for stopping an arm, and the conduct of an interim analysis.

The dose-expansion Part B is based on efficacy evaluable patients (Section 7.7.8 and Section 8.2.2). Patients identified as not efficacy evaluable will be replaced.

The doses for the combination treatments (AZD9150/MEDI4736 and AZD5069/MEDI4736) will have been established in Part A of the study. In the case of the Arm B4 post-interim analysis, the dose of AZD5069 will be 80 mg BID alternate dosing schedule.

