7.2.2 Administration of AZD5069

When given in combination with MEDI4736 (Arms A2, A3, A7, B2, B4, and B6): AZD5069 will be administered as 40 mg BID starting with Day -7 of the 7-day lead-in period at the defined dose in each treatment Arm as described in the study design. Following the lead-in period, patients will receive BID dosing of AZD5069 daily for a 28-day cycle. On days when both AZD5069 and MEDI4736 are given, the morning dose of AZD5069 is administered at least 30 minutes before starting infusion of MEDI4736. For Arm A5 specifically, the sequence of dosing for first 4 cycles would be AZD5069 followed 30 minutes later by tremelimumab infused over 1 hour (± 10 minutes) followed by MEDI4736 infused over 1 hour (± 10 minutes). As discussed in the study design, Arms A5, A7, and food effect substudy will not open for enrolment. In all cases, AZD5069 should be administered either 2 hours before or 2 hours after (with ± 2 hours window) food consumption at approximately the same time each day.

Tremelimumab will be administered at 1mg/kg (once Q4W), and the infusion duration will be approximately 1 hour. The MEDI4736 infusion at 20 mg/kg (once Q4W), will start approximately 1 hour after the end of infusion of tremelimumab, and the infusion will be administered over approximately 1 hour (a window of ± 10 minutes will be allowed). The dose of AZD5069 will be 80 mg BID alternate dosing schedule. Tremelimumab will be infused for a total of 4 months (up to 4 doses). After completion of the initial 4 doses of tremelimumab, patients will continue to receive AZD5069/MEDI4736 as in Arm A2. The first AZD5069/MEDI4736 dose will be given 1 day after the last received dose of AZD5069 of a cycle (Week 4 dose) with MEDI4736 and tremelimumab combination therapy. In the case of the Arm B4 post-interim analysis, the dose of AZD5069 will be 80 mg BID alternate dosing schedule.

When given alone (treatment arm B6 in Part B): AZD5069 will be administered as a fixed PO at flat doses PO BID starting with Day -7 of the 7-day lead-in period. AZD5069 should be administered either 2 hours before, or 2 hours after food (± 2 hours). Dose should be taken on an empty stomach (unless specified for a particular visit for monotherapy arm patients) at approximately the same time each day.

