Additional dose combinations not listed in the table may be explored based on emerging safety, tolerability, and/or pharmacokinetic data. All dose combinations will be determined by the SRC. Figure 7, and Figure 8 provide dosing guidelines for Arms A in Part A and for Arm B2 (post first 20 patients) and Arm B4 (post-interim analysis) in Part B. For Part B, AZD5069 will be administered at 40 mg BID.

Figure 6 Dose-reduction levels for treatment Arm B8

[figure not shown]
If body weight decreases to less than 30 kg, weight-based MEDI4736 dosing (20 mg/kg Q4W) will be implemented. No other dose-reductions will be permitted for MEDI4736 for B8.

- AZD9150 Dose level -1: 300 mg Q2W
- AZD9150 Dose level -2: 200 mg Q2W

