In anti-PD-(L)1 pretreated patients, approximately 10 to 52 patients will be treated in each of the 2 combination therapy arms (B1, B2). In anti-PD-(L)1 naïve patients, approximately 12 to 35 patients will be treated in each of the 2 combination therapy arms (B3 or B4). If in Arm B4, the arm is stopped due to lack of efficacy at the IA (following N=20) a higher dose may be tested under the original sample size requirements (N=35) so the total number of patients in Arm B4 would then be N=55 (N=20 from the original IA and N=35 under the original design for Arm B4). In anti-PD-(L)1 naïve patients, 12 patients will be treated in each of the 2 monotherapy arms (B5, B6). In addition, Arms B7 and B8 each will enroll up to 48 patients who have not received any PD-L1 therapies and have received no prior systemic treatment for RM SCCHN. As a result, the total number of patients in Part B will be between 207 and approximately 255.

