### Anti-PD-(L)1 Pretreated Population

Patients with prior anti-PD-(L)1 antibody exposure who have also been excluded by the Investigator for treatment with AZD5069 will be assigned to the following treatment arm:

- Treatment arm B1: AZD9150 3 mg/kg QW in combination with MEDI4736 20mg/kg Q4W (anti-PD-(L)1 pretreated population)

Patients with prior anti-PD-(L)1 antibody exposure who have **not** been excluded by the Investigator for treatment with AZD5069 will be assigned via an interactive web-based randomization system (IWRS) in a 1:1 ratio to 1 of the following 2 treatment arms:

- Treatment arm B1: AZD9150 3 mg/kg QW in combination with MEDI4736 20mg/kg Q4W (anti-PD-(L)1 pretreated population)
- Treatment arm B2: AZD5069 80 mg BID in combination with MEDI4736 20mg/kg Q4W (anti-PD-(L)1 pretreated population)

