### Anti-PD-(L)1 Naïve Population

Patients with **no** prior anti-PD-(L)1 antibody exposure who have been excluded by the Investigator for treatment with AZD5069 will be assigned via an IWRS in a 2:1 ratio to 1 of the following 2 treatment arms:

- Treatment arm B3: AZD9150 3 mg/kg QW in combination with MEDI4736 20mg/kg Q4W (anti-PD-(L)1 naïve population)
- Treatment arm B5: AZD9150 alone (anti-PD-(L)1 naïve population)

Patients with **no** prior anti-PD-(L)1 antibody exposure who have **not** been excluded by the Investigator for treatment with AZD5069 will be assigned via an IWRS in a 2:2:1:1 ratio to 1 of the following 4 treatment arms:

- Treatment arm B3: AZD9150 3 mg/kg QW in combination with MEDI4736 20mg/kg Q4W (anti-PD-(L)1 naïve population)
- Treatment arm B4: AZD5069 40 mg BID in combination with MEDI4736 20mg/kg Q4W (anti-PD-(L)1 naïve population)

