## Statistical Analysis Plan

### 8. EFFICACY

The following efficacy endpoints will be summarized and analyzed in dose-escalation Part A and dose-expansion Part B:

- Tumour response according to RECIST criteria version 1.1
- Objective response rate (ORR)
- Best overall response rate (BoR)
- Duration of response (DOR)
- Disease control rate (DCR)
- Progression-free survival (PFS)
- Overall survival (OS)

Additionally, survival at 12 months (OS-12) and changes in tumour size will be summarized in Part B.

For dose-escalation Part A, all efficacy data will be summarized by treatment group using descriptive statistics only.

For dose-expansion Part B, all efficacy data will be summarized by treatment group using descriptive statistics and two-sided 80% confidence intervals (CIs) will be provided for the parameter estimates.

No inferential analyses will be conducted to compare the efficacy between treatment groups in either Part A or Part B.

All efficacy data will be analyzed using the Efficacy Set.

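### Arm B4 may hold two AZD5069 regimens, divided at its efficacy interim analysis, but the SAP labels the whole arm 40 mg BID and gives it one ORR

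*Protocol*

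**What the plan says.** **Protocol, B4.** The synopsis plans B4 at 40 mg BID with 12 to 35 patients and an interim analysis at 20. It allows extension to 55 if the dose is changed to 80 mg BID at that analysis. Section 8.2.2 ties this to failure: "If in Arm B4, the arm is stopped due to lack of efficacy at the IA (following N=20) a higher dose may be tested". It counts the total as "N=55 (N=20 from the original IA and N=35 under the original design for Arm B4"). Section 4.2.2 states the dose with no such condition: "In the case of the Arm B4 post-interim analysis, the dose of AZD5069 will be 80 mg BID alternate dosing schedule". Section 7.2.2 repeats that sentence. Section 8.2.2 also continues B4 to 35 patients if at least 5 of the first 20 respond.

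**SAP, B4.** The arm is defined as "Treatment arm B4: AZD5069 40 mg BID in combination with MEDI4736 20mg/kg Q4W". For Part B, "all efficacy data will be summarized by treatment group using descriptive statistics", and SAP 8.2.2 gives ORR with an exact two-sided 80% interval on that basis. Protocol 8.10 presents Part B by anti-PD-(L)1 status and treatment arm, with one entry for B4. SAP 6.4 plans no subgroups. SAP 6.1.1 regroups B3 and B7 patients by line of treatment but has no comparable rule for dose in B4.

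**B2.** The statements conflict.
- The SAP has "Treatment arm B2: AZD5069 80 mg BID in combination with MEDI4736 20mg/kg Q4W", and the protocol synopsis agrees in its arm summary.
- Protocol 7.2.2, for a list of arms that includes B2, says "AZD5069 will be administered as 40 mg BID starting with Day -7 of the 7-day lead-in period". The synopsis dosing section has the same.
- Protocol Table 4 lists both doses for B2 and B4.
- The note to Figure 5 in Protocol 7.7.1 applies the Figure 7 and 8 guidance "for Arm B2 (post first 20 patients) and Arm B4 (post-interim analysis) in Part B".
- The titles of Figures 7 and 8 name only A3 and B4.

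**The concern.** ORR per arm is the Part B primary endpoint. A B4 row that joins 20 patients started at 40 mg BID with up to 35 started at 80 mg BID estimates neither regimen. The SAP would print it under the dose that the minority received. The division is also not neutral. On the route in Protocol 8.2.2, the second cohort exists only because the first missed an efficacy rule, so the number of responses in the first 20 is constrained. The safety tables use the same arm labels, although neutropenia decided how Part A handled 40 and 80 mg BID. Whether B4 is split should be settled in the SAP before the results are seen.

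**Working it through.** **1. The plan's own figure.** 20 + 35 = 55, as Protocol 8.2.2 states. Share on the second regimen: 35/55 = 64%.

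**2. What the first 20 must look like.** The interim analysis takes place only if predictive probability is at least 20% after patient 19 (Protocol 8.2.2; SAP 3.6.2). The SAP 3.6.2 formula, with x responses in 19, sums over k = 0 to 19:

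P(X1 = k | x/19) × P(X2 ≥ 8 − x | μ_k), where X1 ~ Bin(19, x/19), X2 ~ Bin(16, μ_k) and μ_k = k/19 (0.5/19 at k = 0, 18.5/19 at k = 19).

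| Responses in 19 | Predictive probability of at least 8 of 35 | Action |
|---|---|---|
| 3 | 15.8% | stop |
| 4 | 43.6% | go to interim analysis |

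An arm that reaches the interim analysis therefore has at least 4 responses. Missing 5 of 20 means at most 4. The first 20 are then exactly 4/20 = 20.0%.

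**3. Average pooled ORR at N = 55.** (4 + 35 × p80)/55, where p80 is the assumed true ORR at 80 mg BID.

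| p80 (assumed) | Pooled average | Difference from p80 |
|---|---|---|
| 20% | (4 + 7.00)/55 = 20.0% | 0 |
| 25% | (4 + 8.75)/55 = 23.2% | −1.8 points |
| 35% | (4 + 12.25)/55 = 29.5% | −5.5 points |

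**4. What a split would show.** Illustration with 4/20 and 10/35, exact 80% intervals:

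| Row | ORR | 80% interval |
|---|---|---|
| Pooled, 14/55 | 25.5% | 17.8 to 34.5 |
| 40 mg BID, 4/20 | 20.0% | 9.0 to 36.1 |
| 80 mg BID, 10/35 | 28.6% | 18.6 to 40.6 |

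**5. Sensitivity to the stopping formula.** SAP 3.6.2 also refers to a beta-binomial posterior with a non-informative prior. With a Beta(1,1) prior, 3 of 19 gives 22.3% and would continue, so the first 20 could hold 3 or 4 responses. At 3/20 the pooled averages are (3 + 8.75)/55 = 21.4% and (3 + 12.25)/55 = 27.7%, which are 3.6 and 7.3 points low.

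**6. The unconditional wording.** If the 80 mg BID statement in Protocol 4.2.2 and 7.2.2 also covers an arm that passes with at least 5 of 20, then 35 − 20 = 15 patients would follow on the other regimen. The 8-of-35 criterion would be judged on a 20 + 15 mixture.

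**The case against.** **The change is a contingency.** The synopsis and Protocol 8.2.2 make it conditional, and the unconditional sentences can be read as stating the dose for that case. Enrolment is closed, and the documents do not say whether B4 was switched. This stands: the mixture is possible, not established.

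**The SAP does not require pooling.** SAP 6.1 uses treatment group and dose level as the denominator. SAP 6.1.1 shows patients with a dose modification under their initially assigned dose group. The table shells are in a separate document. These provisions leave room for a split, but none defines a dose level within B4, and the dose-modification rule does not address cohorts that start on different regimens.

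**Protocol 8.2.2 already separates the criterion.** It tests the higher dose under the original requirement of 35, apart from the first 20. That stands for the conditional reading. The SAP does not carry it over, and the wording in Protocol 4.2.2 blurs it.

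**Part B is descriptive**, with 80% intervals and no comparison between arms. This limits the consequence, but a descriptive ORR still needs the right regimen beside it.

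**Two stronger readings are tempting.** A reader might infer that B2 too was planned to move from 40 to 80 mg BID after 20 patients. That rests on Table 4 and the Figure 5 note. The synopsis arm summary and the SAP give 80 mg BID alone, and the 40 mg sentence in Protocol 7.2.2 is generic: it also covers A3, an 80 mg arm. A reader might also condition only on missing 5 of 20. With true ORRs of 10% and 25%, that gives a pooled average of 19.3%, about 6 points low. That calculation ignores the stops from patient 12 to 19, which remove the arms with 3 or fewer responses.

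**Conclusion.** The gap is real for B4. The protocol provides for two AZD5069 regimens in one arm, the SAP gives the arm one dose label and one primary ORR, and nothing in the SAP separates the cohorts. If the change was made, up to 64% of the arm would be mislabelled. The pooled ORR would understate the 80 mg rate by 1.8 points at a true 25% and by 5.5 points at a true 35%, with no shift on average at 20%. These sizes assume independent binomial responses, the SAP 3.6.2 formula applied strictly at each patient, a full second cohort of 35, and illustrative response rates. The mislabelling depends on none of these except the full cohort size.

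For B2 the documents support only a contradiction in the stated dose. They do not establish a mixed estimate. Nor do they show that the B4 change took place.

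**What to change.** - In SAP 6.1.1 and 8.2.2, report B4 by initially assigned AZD5069 regimen: N, ORR and exact 80% interval for each, and the same split in the main safety tables. Any pooled row should be marked as supportive. If no patient started on the second regimen, say so.
- State in the SAP that the 8-of-35 criterion is judged within one regimen, as Protocol 8.2.2 implies.
- Reconcile the conditional B4 wording (synopsis, Protocol 8.2.2) with the unconditional wording (Protocol 4.2.2, 7.2.2).
- Reconcile the B2 dose statements: the synopsis arm summary and SAP 3.4.2 against the synopsis dosing section, Table 4, Protocol 7.2.2 and the Figure 5 note. If B2 proves to contain two regimens, apply the same split.

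This review takes no position on which dose or schedule is right. The cost is SAP wording and extra table columns from data already collected. The price is smaller groups: in the illustration, the interval width goes from 34.5 − 17.8 = 16.7 points pooled to 36.1 − 9.0 = 27.1 and 40.6 − 18.6 = 22.0 points.
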